8.3.5 Internal Safety Review Committee (Part A)

The voting members of the iSRC will consist of the Principal Investigator, the CTC Medical Monitor and the Sponsor's Medical Representative. In addition, the trial clinical research manager, the trial pharmacokineticist and additional Sponsor representatives will be invited as appropriate and function as non-voting members. Other internal or external experts may be invited and consulted by the iSRC as appropriate.

Before initiating a new dose cohort, all participants in the previous cohort must have been treated and all available safety, tolerability, and plasma concentration data up until and including 24 hours after dosing must have been evaluated by the iSRC. After collection of the last available 24-hour data, there will be at least 1 week between dose escalations. In case of dropouts, available data for the dropouts will be included in the iSRC evaluation. If the GZ21T drug is considered safe and tolerable, the recommended next dose level, based on the predicted exposure, will be provided to the Sponsor in writing. Based on the emerging safety and plasma PK data, the amount of required data to be reviewed after each completed cohort may be adjusted. Likewise, the number of dose levels and planned sampling times may also be adjusted. These adjustments will be documented in non-substantial modifications to the CTP. Details regarding the timing of iSRC reviews and the data to be reviewed will be provided in a separate iSRC charter.

Sentinel dosing will be applied. The first 2 participants in each cohort will receive either GZ21T or placebo as randomised. After the sentinel participants, at least 24 hours must pass before dosing of the remaining participants to give sufficient time for the observation of any reactions.

An adaptive dosing strategy will be applied to allow for a flexible and safe dose escalation. The planned dose escalation is outlined in Section 8.3.2. The actual doses administered in each cohort will be guided by the iSRC recommendations based on the available safety, tolerability, and PK data, as described above. Every dose step is thus adjustable and the recommendation to the Sponsor may be to continue with a higher or lower dose than the planned dose, to repeat the same dose level, to continue with an intermediate dose level, or to stop dosing.

The recommendations of the iSRC will be made in consensus between the iSRC members and documented as appropriate. In case of disagreement between the voting members, the most conservative approach will be taken. Repeating a dose level will not be allowed if any of the dose escalation-stopping criteria described in Section 8.3.4 have been met.

The treatment code for individual participants may be requested to be broken by the iSRC voting members during the assessment process (partial unblinding) in accordance with the stopping criteria described in Section 8.3.4 to enable their decision on continued dosing of further cohorts or to stop the dose escalation. The medical staff will still be blinded for the treatments (active drug or placebo) to be administered in the subsequent cohorts in order to minimise bias. If unblinding was considered necessary, the iSRC meeting may consist of a closed part and an open part.

9 TRIAL POPULATION

Prospective approval of deviations from the eligibility criteria, also known as protocol waivers or exemptions, is not permitted.

9.1 Recruitment

Participants will be recruited from CTC's database of healthy volunteers, as well as from strategic marketing campaigns. Advertisements in social media and other media (newspapers, internet, radio, local distribution of flyers *etc.*) will be used to reach the target audience. The advertisement texts authorised by the Independent Ethics Committee (IEC) will be used to create all materials (digital, radio and/or print) for recruitment.

9.2 Screening and enrolment log

Investigators must keep a record of all screened participants even if they were not subsequently included in the trial. This information is necessary to verify that participants were selected without bias. The reason for screening failure should be stated for all participants screened but not included. The reason for withdrawal should be stated for all participants who were included but did not complete the trial.

A screening number generated automatically in the electronic case report form (eCRF) will be allocated to each participant in connection to the informed consent process at the screening visit (Visit 1). The screening number will allow the identification of participants irrespective of their possible eligibility for the trial.

Eligible participants will be assigned a 3-digit randomisation number prior to the first IMP administration. For details, refer to Section 9.9.

If a participant cannot receive the planned treatment with the IMP within 28 days after screening (*i.e.*, the time interval between signing informed consent until the first administration of IMP) the participant should be rescreened before proceeding with the trial.

9.3 Number of participants

Part A: Approximately, 64 potential participants will be screened to achieve 32 randomised participants (4 cohorts, 8 participants per cohort randomised in a 6:2 ratio).

Part B: Approximately 18 potential participants will be screened to achieve up to 9 included participants.

For the replacement of participants who discontinue the trial, see Section 9.8.3.

9.4 Inclusion criteria

For inclusion in the trial, the participants must fulfil the following criteria:

1. Willing and able to give written informed consent for participation in the trial.
2. Healthy male or female participant aged 18 to 70 years, inclusive.
3. Body Mass Index (BMI) ≥ 18.5 and $\leq 30.0 \text{ kg/m}^2$ at the time of the screening visit.
4. **WOCBP** must practice abstinence from heterosexual intercourse (only allowed when this is the preferred and usual lifestyle of the participant) or must agree to use a highly effective method of contraception with a failure rate of $<1\%$ to prevent pregnancy from at least 2 weeks prior to the administration of IMP to 4 weeks after the last administration of IMP.

In addition, any male partner of a female participant must, unless he is sterile (*e.g.*, has undergone vasectomy), agree to use a condom from the first administration of IMP until 4 weeks after the last administration of IMP.

The following are considered highly effective methods of contraception:

- combined (oestrogen and progestogen-containing) hormonal contraception associated with inhibition of ovulation (oral, intravaginal, transdermal),
- progestogen-only hormonal contraception associated with inhibition of ovulation (oral, injectable, implantable),
- intra-uterine device [IUD] or intra-uterine hormone-releasing system [IUS]).

WOCBP must refrain from donating eggs from the first IMP administration until 3 months after the last IMP administration.

Women of non-childbearing potential are pre-menopausal females who have undergone any of the following surgical procedures; hysterectomy, bilateral salpingectomy, or bilateral oophorectomy, or who are post-menopausal defined as 12 months of amenorrhea (in questionable cases a blood sample with detection of follicle-stimulating hormone [FSH] >25 IU/L is confirmatory).

Male participants, if not sterile (*e.g.*, vasectomised), must be willing to use a condom or practice sexual abstinence from heterosexual intercourse (only allowed when this is the preferred and usual lifestyle of the participant) to prevent pregnancy and drug exposure of a partner and refrain from donating sperm from the first administration of IMP until 3 months after the last administration of IMP. Any female partner of a non-vasectomised male participant who is of childbearing potential must use contraceptive methods with a failure rate of < 1% to prevent pregnancy (see above) from at least 2 weeks prior to the first administration of IMP to 4 weeks after the last administration of IMP.

9.5 Exclusion criteria

Participants must not enter the trial if any of the following exclusion criteria are fulfilled:

1. History of any clinically significant disease or disorder which, in the opinion of the Investigator, may either put the participant at risk because of participation in the trial or influence the results or the participant's ability to participate in the trial.
2. Any clinically significant illness, medical/surgical procedure, or trauma within 4 weeks of the administration of IMP.
3. Any clinically significant abnormalities regarding physical examination, vital signs, 12- lead ECG, and laboratory values at the time of the screening visit, as judged by the Investigator.
4. Malignancy within the past 5 years, including removal of basal cell carcinoma.
5. Any planned major surgery within the duration of the trial.
6. Any skin condition including tattoos that may limit the evaluation of *e.g.*, local tolerability as judged by the Investigator.
7. History of chronic urticaria, known history of urticaria triggered by specific factors or currently experiencing an episode of urticaria within the past 3 months.
8. History of psoriasis, atopic eczema and similar conditions, as judged by the Investigator.
9. Presence of body hair or tattoos on the intended application areas, which in the opinion of the Investigator could interfere with local tolerability assessments.

10. Females who are pregnant, currently breastfeeding, or intend to become pregnant during the course of the trial.
11. Any positive result at the screening visit for serum hepatitis B surface antigen, hepatitis B and C antibodies and/or human immunodeficiency virus (HIV).
12. After 10 minutes of supine rest at the screening visit, any vital signs values outside the following ranges:
 - Systolic blood pressure: <90 or \geq 140 mmHg, or
 - Diastolic blood pressure <50 or \geq 90 mmHg, or
 - Pulse <40 or >90 bpm
13. Prolonged QTcF (>450 ms), cardiac arrhythmias or any clinically significant abnormalities in the resting ECG at the screening visit, as judged by the Investigator.
14. History of severe allergy/hypersensitivity or ongoing allergy/hypersensitivity, as judged by the Investigator, or history of hypersensitivity to drugs or food with a similar chemical structure or class to GZ21T.
15. Regular use of any prescribed or non-prescribed medications, including antacids, analgesics, herbal remedies, within 2 weeks prior to the (first) administration of IMP, except occasional intake of paracetamol (maximum 2000 mg/day and not exceeding 3000 mg/week), as well as nasal decongestants without cortisone, antihistamine, or anticholinergics for a maximum of 10 days, at the discretion of the Investigator.
16. Unwillingness to abstain from the use of topical treatment (including but not limited to corticosteroids, calcineurin inhibitors, vitamin D analogues, and retinoids) at the application site within 1 week prior to Day 1 and from the use of moisturising ointment cream, emollients, oils (including shower oil) or sunscreen within 24 hours prior to Day 1 until 1 week after IMP administration.
17. Planned treatment or treatment with another investigational drug within 3 months prior to Day 1. Participants who consented and screened but were not dosed in previous clinical trials are not to be excluded.
18. Current smokers or users of nicotine products. Irregular use of nicotine (e.g., smoking, snuffing, chewing tobacco) less than 3 times per week is allowed before screening visit.
19. Positive screening result for drugs of abuse or alcohol at the screening visit or on admission to the trial site prior to the administration of the IMP. (Positive results that are expected given the participant's medical history and prescribed medications can be disregarded as judged by the Investigator.)
20. History of alcohol abuse or excessive intake of alcohol, history or presence of drug abuse including anabolic steroids, as judged by the Investigator
21. Plasma donation within approximately 1 month of screening or blood donation (or corresponding blood loss) during the last 3 months prior to screening, at the discretion of the Investigator.
22. The Investigator considers the participant unlikely to comply with trial procedures, restrictions and requirements.

9.6 Restrictions during the trial

Participants must be willing to comply with the restrictions as outlined in 9.6.1 and 9.6.2.

9.6.1 General restrictions

1. **Contraception requirements:** Participants are expected to use contraceptive methods in accordance with inclusion criterion #4 or practice abstinence from heterosexual intercourse (only allowed when this is the preferred and usual lifestyle of the participant) during the clinical trial.
2. **Alcohol:** Consumption of alcohol is not allowed within 48 hours prior to admittance to the trial site including the end-of-trial visit.
3. **Drugs of abuse:** The use of drugs of abuse is not allowed from the screening visit to the end-of-trial visit. In addition to the urine drug screens described in the schedule of events, additional random testing can be performed at the site visits.
4. **Nicotine:** Smoking or use of nicotine products (e.g., snuff, chewing tobacco) are not allowed from the screening visit to the end-of-trial visit.
5. **Exercise:** The participants will be asked to abstain from strenuous exercise, defined as greater than 70% of the maximal pulse rate for ≥ 1 hour, for 48 hours prior to each trial visit.
6. **Blood donation:** The participants must not donate blood or plasma from the screening visit until 3 months after the final medical examination at the end-of-trial visit.
7. **Participation in other clinical trials:** The participants are not allowed to participate in any other interventional clinical trial from the screening visit until the end-of-trial visit.
8. **Leaving the trial clinic:** Participants are not allowed to leave the trial site during trial visits unless authorised by the trial personnel.
9. **Moisturising creams:** Participants must have abstained from using moisturising ointments, creams, or emollients (including shower oil and sunscreen) on the area to be treated for 24 hours prior to treatment on Day 1, until the end-of-trial visit.
10. **Showering:** Participants must refrain from washing the treated area or taking a shower from the IMP administration until the 24-hour assessment on Day 2 (Part A).
11. **Sun protection:** Protection from the sun is required from the IMP administration until the end-of-trial visit (Day 7). Participants are recommended to:
 - Stay in the shade, especially during the sun's peak hours of 10 AM to 4 PM.
 - Wear clothing that covers the treated skin area.
 - Abstain from the use of tanning beds.

9.6.2 Prior and concomitant therapy

9.6.2.1 Prohibited medications

The regular use of any prescribed or non-prescribed medication within 2 weeks prior to the administration of IMP is not allowed, as judged by the Investigator. This includes antacids, analgesics and herbal remedies.

Topical treatments are not allowed at the application site within 1 week prior to IMP administration.

The use of any prescribed or non-prescribed medication from the administration of IMP until the end-of-the trial visit will not be allowed except as detailed below.

9.6.2.2 *Allowed medications*

- Paracetamol in doses up to 2000 mg/day for a maximum of 3 consecutive days. If this amount of paracetamol is insufficient for the treatment of the participant, withdrawal should be considered.
- Nasal decongestants without cortisone, antihistamine, or anticholinergics for a maximum of 10 days.
- Non-steroidal anti-inflammatory drugs (NSAIDs) intermittent use for dysmenorrhoea and dysmenorrhoea-associated symptoms, as judged by the Investigator.
- Contraceptives, as defined in inclusion criterion #4.
- Vitamins and minerals.

As detailed in exclusion criterion #18, a positive drug-screen will exclude a participant from participation in the trial. However, positive results that are expected given the participant's medical history and prescribed medications (e.g., opioid analgesics or attention deficit hyperactivity disorder [ADHD] medications) can be disregarded as judged by the Investigator.

9.7 **Screen failures**

Screen failures are defined as participants who consent to participate in the clinical trial but do not fulfil all eligibility criteria and are not subsequently included in the trial. A minimal set of screen failure information is required to ensure transparent reporting of screen failure participants. Minimal information includes documentation of signed and dated informed consent form (ICF) and reason(s) for screening failure.

Participants who do not meet the criteria for participation in this trial may be rescreened.

Re-screening can be performed once if any of the following were reasons for screening failure or non-randomisation, as judged by the Investigator:

- Practical reasons.
- Non-significant medical conditions (e.g., influenza, nasopharyngitis).
- Reserve participants not used in a previous group of participants.

For participants who are rescreened, a new screening number will be assigned and a new, signed ICF must be collected.

9.8 **Participant withdrawal**

9.8.1 *General withdrawal criteria*

Participants are free to voluntarily discontinue their participation in the trial, *i.e.*, withdraw consent, at any time and for whatever reason without affecting their right to an appropriate follow-up investigation or their future care. If possible, the reason for withdrawal of consent should be documented in the eCRF.

Participants may also be discontinued from the trial at any time at the discretion of the Investigator.

Reasons for discontinuation can include:

- AE (as judged by the Investigator and/or Sponsor).
- Death.
- Logistical problem.
- Lost to follow-up.
- Non-compliance with study device.
- Non-compliance with trial drug.
- Non-compliance with trial schedule.
- Physician decision.
- Pregnancy.
- Protocol deviation.
- Technical problems.
- Withdrawal of consent (participant decision).
- Other.

9.8.2 Procedures for discontinuation of a participant from the trial

A participant who prematurely discontinues participation in the trial will always be asked about the reason(s) for discontinuation and the presence of any AEs. If a participant withdraws consent, the Investigator must ask the participant if he/she is willing, as soon as possible, to be assessed according to the procedures scheduled for the end-of-trial visit. Any ongoing AEs will be followed up as described in Section 11.3.1.16.

The primary reason for discontinuation/early withdrawal must be specified in the eCRF and final drug accountability must be performed. If the reason for discontinuation was an AE, the AE must be specified in the eCRF.

9.8.3 Participant replacement

Participants who are prematurely withdrawn from the trial for any reason except the occurrence of AEs assessed as possibly or probably related to the trial treatment may be replaced.

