11.3.1.11 Assessment of causal relationship

The Investigator must assess the causal relationship between an AE and the use of the IMP, using the definitions below. Each assessment should be recorded in the AE log of the eCRF.

Not related	There is no evidence of causal relationship with the IMP.
Unlikely related	The event has little evidence of causal relationship to the IMP.
Possible related	The event has a suggestive causal relationship to the IMP, and an alternative aetiology is equally or less likely.
Probable related	The event has a strong causal relationship to the IMP or recurs on re-challenge, and another aetiology is unlikely or significantly less likely.
Definitely related	The event is clearly related to the IMP.

An AE is considered causally related to the use of the IMP when the causality assessment is probable or possible.

11.3.1.12 *Outcome of adverse event*

The Investigator must assess the outcome of an AE using the definitions below and record it on the AE log of the eCRF.

Recovered/resolved	The participant has recovered completely, and no symptoms remain.
Recovering/resolving	The participant's condition is improving, but symptoms remain.
Recovered/resolved with sequelae	The participant has recovered, but some symptoms remain (e.g., the participant had a stroke and is functioning normally, but has some motor impairment).
Not recovered/not resolved	The participant's condition has not improved, and the symptoms are unchanged (e.g., atrial fibrillation has become chronic).
Fatal	
Unknown	

11.3.1.13 *Action taken with trial treatment*

The Investigator must document the action taken with trial treatment using the definitions below and record it on the AE log of the eCRF.

Dose increased N/A

Dose not changed

Dose reduced N/A

Drug interrupted

Drug withdrawn N/A

Not applicable

Unknown

11.3.1.14 *Reporting of serious adverse events*

The Investigator must report SAEs within **24 hours** of awareness to the Sponsor or its designee, this includes both initial information and any subsequent relevant/significant follow-up information to a previously reported SAE.

The primary mechanism for reporting an SAE will be via the eCRF. When the Investigator classifies the event as "serious" in the eCRF, and signs off the event, an automatic e-mail alert is sent to the Sponsor or its designee, and any other predefined recipients.

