17.6 Analysis of primary endpoints

17.6.1 Adverse events

An overview of all AEs, including SAEs, intensity, relationship to IMP, and deaths will be presented by part, cohort, treatment, and overall. The incidence of AEs and SAEs will be summarised by SOC and PT by treatment, cohort and overall. An overview of any treatment-related (probably/possibly related) AEs will be summarised by SOC and PT and by treatment, cohort and overall if considered appropriate. All AE data will be listed by participant and include the verbatim term entered by the Investigator.

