4.4 Participant replacement

Participants who were prematurely withdrawn from the trial for any reason except the occurrence of AEs assessed as possibly or probably related to the trial treatment may have been replaced.

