6 CHANGES FROM THE CLINICAL TRIAL PROTOCOL

Changes to the planned analyses and the timing of these are summarised in Table 5.

Table 5 Changes in the planned statistical analyses

Change category	Timing of change	Description of change	Reason for change
Change in the SAP compared to the CTP	Prior to DBL	
A minor change has been made to the phrasing of the definitions for FAS and PKAS. This change does not affect whether participants are included in the analysis sets or not. See Table 4 for details.
 
In section 9.1.1, definitely related AEs has been added to the definition of causally related AEs, which is missing from sections 11.3.1.11 and 17.6.1 of the CTP.
 
Frequency tables for safety laboratory interpretations have been added.
 
The overall/total column has been removed from all safety tabulations, except for AEs and LTs.
	To minimise confusion. “Definitely related” was missing from the AE definitions in sections 11.3.1.11 and 17.6.1 of the CTP To provide a better overview of the safety laboratory data. Redundant information.

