9.1 Analysis of the primary endpoints

9.1.1 *Adverse events*

An overview of all AEs, including SAEs, intensity, relationship to IMP, and deaths will be presented by part, cohort treatment, and overall. The incidence of AEs and SAEs will be summarised by SOC and PT by treatment, cohort and overall. A summary of any treatment-related (probably/possibly/definitely related) AEs will be summarised by SOC and PT and by treatment, cohort and overall if considered appropriate.

9.1.2 *Local tolerability*

An overview of all local tolerability reactions including maximum intensity grade per local tolerability reaction will be presented by part, cohort, treatment, and overall. Intensity grade for each local tolerability reaction will also be presented by cohort, treatment, and overall using a frequency table. Changes from baseline in intensity grade at each time point will be summarised in a shift table.

9.1.3 *Vital signs*

Vital signs will be summarised by treatment and cohort, and by assessment time point. Data will be presented with absolute and percent change from baseline. Vital signs data (blood pressure and pulse) for eligibility (screening) in Part B will only be listed.

9.1.4 *Electrocardiogram*

All ECGs will be categorised as "normal", "abnormal, not clinically significant", or "abnormal, clinically significant" (as judged by the Investigator) and summarised by treatment and cohort, and by assessment time point using frequency tables. Changes over time will be presented using a shift table if considered appropriate. All measured ECG values will be summarised by treatment, cohort and overall, and assessment timepoint with absolute and percent change from baseline. ECG data for eligibility (screening) in Part B will only be listed.

9.1.5 *Safety laboratory*

Safety laboratory data will be summarised by treatment and cohort, and by assessment time point with absolute and percent change from baseline.

All safety laboratory measurements will be categorised as "normal", "abnormal, not clinically significant", or "abnormal, clinically significant" (as judged by the Investigator) and

summarised by treatment and cohort, and by assessment time point using frequency tables. Safety laboratory data for eligibility (screening) in Part B will only be listed.

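### The replacement rule in Protocol 9.8.3 leaves out definitely related AEs, so it permits replacement after them; the SAP corrected this omission in two other sections but not here

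*Protocol*

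**What the plan says.** Protocol 9.8.3 allows replacement after early withdrawal for any reason "except the occurrence of AEs assessed as possibly or probably related to the trial treatment may be replaced". SAP 4.4 gives the same rule in the past tense, ending "except the occurrence of AEs assessed as possibly or probably related to the trial treatment may have been replaced".

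The causality scale in Protocol 11.3.1.11 has five levels: not, unlikely, possible, probable and definitely related. The last is defined by the words "The event is clearly related to the IMP". The same section then defines relatedness without that level: "An AE is considered causally related to the use of the IMP when the causality assessment is probable or possible". Protocol 17.6.1 follows suit and summarises "treatment-related (probably/possibly related) AEs".

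The SAP noticed this. Its Table 5 records that "definitely related AEs has been added to the definition of causally related AEs, which is missing from sections 11.3.1.11 and 17.6.1 of the CTP", and SAP 9.1.1 now summarises "treatment-related (probably/possibly/definitely related) AEs". The footnotes planned for Tables AE 7 and AE 8 carry the corrected definition. Table 5 does not mention Protocol 9.8.3.

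**The concern.** A rule against replacing people withdrawn for drug-related events keeps a cohort from being topped up after the drug has caused a dropout. As written, the rule applies at the two intermediate levels of relatedness and lapses at the strongest, which is treated like not related or unlikely related.

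The case is not purely theoretical in a topical trial. Protocol 11.3.2 requires qualifying local reactions to be recorded as AEs related to the product but does not say which related level to use. Whether a withdrawal can be replaced could then turn on a choice between probable and definite, with the firmer judgement bringing the weaker restriction.

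At stake is a modest dilution of the AE rate in a small cohort, and a disposition table that would not reveal it: the shells for Tables DS 1 and DS 2 have no row for replacements.

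**Working it through.** **Inputs.** Part A has 4 cohorts of 8, allocated 6:2 (Protocol 9.3). This reproduces the stated total: 4 × 8 = 32, of whom 4 × 6 = 24 receive active and 4 × 2 = 8 placebo. The full analysis set contains every enrolled participant who received product (SAP Table 4), with no exclusion on replacement. There is no formal sample size calculation (Protocol 17.2), so no power figure is affected. All event counts below are assumed for illustration.

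**Step 1: the rule applied to each causality level.**

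| Level | Replacement allowed under 9.8.3 as written | Replacement allowed if related is defined as in SAP 9.1.1 |
|---|---|---|
| Not related | yes | yes |
| Unlikely | yes | yes |
| Possible | no | no |
| Probable | no | no |
| Definitely | **yes** | **no** |

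The two definitions differ only at definitely related.

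**Step 2: effect on a cohort's AE rate.** Let k of the 6 active participants have a definitely related event, withdraw and be replaced, with every replacement on active. Let r of the replacements have the event. All of them are in the full analysis set.

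- Rate without replacement: k/6.
- Rate with replacement: (k + r)/(6 + k).
- k = 1, r = 0: 1/7 = 14.3%, against 1/6 = 16.7%, a fall of 2.4 percentage points.
- k = 2, r = 0: 2/8 = 25.0%, against 2/6 = 33.3%.
- k = 1, r = 1: 2/7 = 28.6%, so a single case can also move the rate up.

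Section 9.8.3 is not limited to Part A. In a Part B cohort of 3, one case with an event-free replacement moves the rate from 1/3 (33.3%) to 1/4 (25.0%).

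**Step 3: is there a systematic direction?** Suppose the true risk is 1/6 for everyone. Given exactly one event, the expected rate after replacement is (1 + 1/6)/7 = 16.7%, which is unchanged. Averaged over all possible numbers of events it is not. Let X be binomial (6, 1/6), with every event leading to withdrawal and one round of replacement. The expected rate is then (7/6) × E[X/(6 + X)]. The terms for X = 1 to 6 are 0.0574, 0.0502, 0.0179, 0.0032, 0.0003 and 0.00001, which sum to 0.1290. Multiplying by 7/6 gives about 15.1%, against 16.7%. The bias is downward and small, even though this scenario has every event replaced.

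**The case against.** The strongest reply is that this is a drafting slip with an obvious intent. The wording of 9.8.3 matches the protocol's own definition of causally related in 11.3.1.11, and the SAP has acknowledged that definition as incomplete. Nobody need read the rule as favouring replacement after a definite reaction, and it says may, not must. That is fair as to intent, but nothing in either document closes the gap for replacement.

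The worst cases are also covered elsewhere. The stopping criteria in Protocol Table 8.3-1 use a threshold of at least possibly related, which includes definite. One related SAE on active, or two severe related AEs on active in one cohort, stops further dosing at that level, and Protocol 8.3.5 then forbids repeating it. What remains in Part A is a definitely related event below those thresholds that leads to withdrawal after a single application. This stands and limits the point.

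Much of the reporting is already planned: withdrawals with reasons, AEs leading to withdrawal, causality by level including definitely related, and listings of discontinued participants. Only the explicit identification of a replacement is missing.

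SAP 4.4 is not a failed correction either. Table 5 concerns planned analyses, whereas replacement is trial conduct, and SAP 4.4 reports the rule that applied. Inserting the missing word there would misdescribe that rule. This also stands.

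A reader might further infer that replacement removes the event from the safety results, that it favours tolerability among completers or in the PK analysis set, or that replacements are selected for tolerance. The documents support none of these. Dosed participants stay in the full analysis set; no completer safety analysis is planned beyond a disposition count; the PK set serves PK endpoints only; and nothing selects replacements by tolerance.

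**Conclusion.** The omission in Protocol 9.8.3 is certain: the rule is wrong as written at one of five causality levels, and the SAP concedes the same fault in two sections without naming this one. The consequence is minor. No event is lost, and the example of 16.7% falling to 14.3% assumes that the withdrawn participant and the replacement both received active and that the replacement is event-free. The documents do not state how a replacement's treatment is allocated. The average downward shift to about 15.1% rests on a true risk of 1/6 and on every event being followed by one replacement, which overstates what is likely after a single dose. The trial is descriptive, so no test or error rate is affected. The documents do not show whether any such replacement took place.

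**What to change.** - **Protocol 9.8.3:** for any remaining or future enrolment, bring the rule into line with the definition of related in SAP 9.1.1, so that it names possibly, probably and definitely related.
- **SAP 4.4:** leave it unchanged, as the record of the rule in force.
- **SAP Table 5:** extend the existing entry on definitely related AEs to note that Protocol 9.8.3 shares the omission.
- **Disposition output:** state whether any participant withdrawn for a definitely related AE was replaced. If so, identify both the participant and the replacement. If none was, one sentence saying so is enough.

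The cost is one line in Table 5 and one disclosure line in the report. If dosing is still under way, the protocol change also needs the numbered modification form described in Protocol 14.7. The SAP's past tense on randomisation and administration suggests, but does not establish, that dosing is complete. If it is, the Table 5 note and the disclosure are the parts that matter for this trial.
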